Implementing Family-Based Treatment for Adolescent Anorexia Nervosa for Providers in Private Practice: A Feasibility Study

Statistical Analysis Plan

NCT04428580

June 9, 2020

DATA ANALYSIS

Aims

Aim 1: The overall aim of the study is to assess the feasibility of conducting a randomized clinical trial comparing two implementation strategies (online training vs webinar training) for training clinicians in private practice in FBT for AN.

Aim 2: Patient outcomes (reflecting therapist effectiveness) will be assessed by comparing patient weight gain from session 1 to 4 of FBT before and after training (target for training effect) and compared between randomized groups.

Aim 3: Validate training effect by examining the association between therapist fidelity to FBT and patient outcomes. We predict that fidelity will be correlated (target validation) with patient outcome. The effects of therapeutic alliance, participation in supervision, and self-efficacy on both fidelity and patient outcome will be explored.

Aim 4: Explore BL factors associated with implementation processes (e.g., prior training, experience, family work).

Data Analytic Plan

The analytic plan for each aim is as follows:

In **Aim 1**, we will first examine how well we can retain clinicians in our study. We will consider retaining 50% by end of study (6 months from the baseline) as neither success nor failure and at least 65% as successful retention. We will employ simple one-sample chi-square test (2-tailed, alpha=.05) comparing the sample retention to 50%. We will then examine whether therapist fidelity and competency in implementing FBT significantly improves from pre training to post training. For this investigation, we will employ longitudinal mixed effects modeling, which enables us to fully utilize outcome data repeatedly measured for most clinicians (3 assessments: 0 (pre), 3 and 6 month). Data points that are missing due to clinician attrition or intermittent dropout will be handled assuming that data are missing at random conditional on observed information. In this procedure, all available cases including the ones with missing information will be included in the analyses. We believe such missing data assumption is reasonable given that we will include variables (e.g., clinician fidelity/competency) supposedly related to attrition in our mixed effects modeling. Nonetheless, as a way of sensitivity analysis, we will conduct mixed effects analyses with and without including other possible predictors of attrition, which we believe is important to support the validity of our study findings as we expect a considerable level of attrition. For estimation of mixed effect models, we will employ maximum likelihood (ML) estimation embedded in the Mplus program.

In **Aim 2**, using the same mixed effects modeling approach, we will examine whether the patient outcome (weight gain) significantly improves from pre to post training.

In **Aim 3**, we will examine the relationship between the changes in clinician outcomes (fidelity/competency) and the change in patient outcome (weight gain). This will be investigated in the latent variable modeling framework, by formally relating the parallel longitudinal processes (esp. by correlating the slopes) of patient and clinician outcomes. This investigation is of particular

interest in our study as it serves as a way of validating the effect of online ET-FBT training on clinician outcomes by correlating them with a clinically relevant patient outcome. Further, the results of this investigation will be the basis for formally investigating clinician outcomes as possible mediator of online ET-FBT training effects on patient outcomes in future randomized studies.

In **Aim 4**, we will explore various baseline variables as possible predictors of pre to post training changes in clinician and patient outcomes. This investigation will also be conducted in the mixed effects modeling framework. The results of this study will inform future randomized studies about possible moderators of online ET-FBT training effects on patient and clinician outcomes.

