# Implementing Family-Based Treatment for Adolescent Anorexia Nervosa for Providers in Private Practice: A Feasibility Study

Study Protocol

NCT04428580

June 9, 2020

We will employ the same recruitment strategy that was successful in our initial study and advertise throughout the United States (US) on the Academy for Eating Disorders (AED) websites, Eating Disorder Research Society (EDRS) listserve, and the National Eating Disorder Association (NEDA) listserve. In addition, we will use Facebook and Twitter advertisements to augment these approaches.

Therapists will be trained in one of two ways for this study: 1) online training x 3 months, followed by expert supervision for 3 months; or 2) recorded webinar training provided in 12 1-hour webinar lectures provided weekly, followed by expert supervision for 3 months. UCSF, listed as a collaborating institute, will aid in training and supervising the participating therapists in one of these two arms of Family-based Treatment training (see description of research activities at UCSF below).

Therapists are eligible to participate if they have completed a masters or doctoral training in their field (psychology, psychiatry, family therapy, social work), are licensed in their respective state, have no reports of malpractice or loss of privileges at relevant clinical institutions, have computer/web access for online training and assessments and no previous 2-day in-person workshop training in FBT, and submit baseline data on weight gain from week 1-4 from a previously treated adolescent with AN they have treated in the last 6 months or alternatively one that they treat within 3 months of the initial screening before starting the training. Therapists who have had previous training in FBT are not eligible to be randomized.

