Therapists will complete an online screen. If they appear to be eligible, an online consent form will be triggered (waiver of documentation included on the application). If they do consent, they will be asked to complete online questionnaires that will amount to be the baseline assessment prior to randomization. Demographic and practice characteristics of all therapists (age, gender, ethnicity, race, months of experience treating eating disorders, specialized trainings, practice setting, payments accepted), self- report of fidelity, knowledge of FBT, skills of FBT using responses to role played videotapes, and expert ratings of fidelity will be collected. The total assessment burden for therapists will be about one hour to an hour and a half for the entire screen, consent, and baseline assessment.

Once this is complete the research team will review the assessment and double check eligibility before randomizing the participant to either arm of training. The research team will then reach out to the therapist to inform them of which arm of training they were randomized to and go over again what that entails as well as get them set up with either:

1) Online training which consists of 10 lectures that are self-paced with a maximum of three months to complete with each lecture bundle comprising of 5- 8 short (about 4 minutes in length), didactic videos that discuss the treatment model and provide mock therapy session video clips (modeling FBT with a typical adolescent AN case), as well as supplementary readings and videotaped role- plays. Enrollees complete each lecture bundle and complete the assignments as they move through the training at their own pace, but to have completed all within the 3-month time frame.

2) Webinar training which consists of 1-hour weekly webinar lectures that essentially is the FBT training that is conducted in person, just recorded. There will be lectures discussing the scientific evidence supporting FBT, how therapists set up treatment for FBT, main interventions used in FBT during each phase, and recorded role-plays illustrating interventions throughout the 3 phases. Enrollees watch each webinar video as it is released weekly over a 12 week (3 month period).

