Weight change in patients treated pre and post-training: Weight change from sessions 1 to 4 will be collected on one adolescent patient with AN treated pre-training (baseline eligibility) and post online ET-FBT per participating therapist during supervision or within 3 months following completion of supervision. No patient identifying information will be collected. This will take 5 minutes to complete. This measure will be used as the main outcome for treatment (patient outcome) efficacy (Aim 2).

Key component skills: Therapists will be asked to view mock therapy session video clips and play the role of the therapist. These clinical videotapes are actors playing families using a script and usually lasting less than three minutes. The therapist in training watches the video and records their verbal intervention response to the clinical scene. The specific skills assessed are related to how effectively the therapist used externalization or agnosticism (as appropriate clinically) and will be scored by expert clinicians using standardized coding. This was the approach used in our preliminary study. This measure will be completed at BL, ~3 months (end of online training-EOT), and end of supervision (EOS) ~6 months. This is a measure of fidelity and change will be correlated with patient weight change outcome (Aim 3) for target validation.

Key component knowledge: This is a brief 10 question multiple choice measure of knowledge of key components of FBT that was used in our preliminary study. These will be conducted at BL, ~3 months (end of online training-EOT), and end of supervision (EOS) ~6 months. This is a measure of fidelity and change will be correlated with patient weight change outcome (Aim 3) for target validation.

Consultation Questions: The brief 8 questions ask participants about their experience with supervision in the research study. This measure will be administrated at ~3 months (end of training-EOT), and end of supervision (EOS) ~ 6 months.

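### Aim 2 promises a comparison of patient weight gain between the randomized arms, but its stated analysis tests only before-to-after improvement and names no arm term

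*SAP*

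**What the plan says.** SAP, Aims, Aim 2: weight gain from session 1 to 4 will be assessed "before and after training (target for training effect) and compared between randomized groups". That is two comparisons, one over time and one between arms.

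SAP, Data Analytic Plan: the section opens with "The analytic plan for each aim is as follows". Its whole entry for Aim 2 reads "using the same mixed effects modeling approach, we will examine whether the patient outcome (weight gain) significantly improves from pre to post training". The approach referred to is the Aim 1 model, a maximum likelihood mixed model that uses all available cases under a missing-at-random assumption.

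Protocol, Treatment Outcome Measures, on weight change: "This measure will be used as the main outcome for treatment (patient outcome) efficacy (Aim 2".

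Protocol, therapist eligibility: therapists must "submit baseline data on weight gain from week 1-4 from a previously treated adolescent with AN", or alternatively supply a case treated within 3 months of screening and before training starts. The team will then "double check eligibility before randomizing the participant to either arm of training".

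**The concern.** Therapists are randomized to online or webinar training, and Aim 2 contains the only between-arm outcome comparison that the SAP commits to. The sentence meant to carry out Aim 2 answers a different question: whether weight gain is better after training than before it.

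An analyst who follows that sentence would report one change over time and no arm difference on the main Aim 2 outcome. An analyst who notices the commitment would have to choose the contrast, the handling of the pre-training value and the patient case without guidance, possibly after seeing the data.

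**Working it through.** **1. Does any other text supply the arm comparison?**

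- Aim 1: a one-sample test of overall retention against 50%, then a model of fidelity and competency at 0, 3 and 6 months that asks about improvement over time. The only extra covariates mentioned are predictors of attrition.
- Aim 2: refers back to the Aim 1 approach and adds no arm term.
- Aim 3: correlates the slopes of clinician and patient outcomes.
- Aim 4: "we will explore various baseline variables as possible predictors of pre to post training changes in clinician and patient outcomes". Allocated arm is not a baseline characteristic of the therapist.
- The Data Analytic Plan never mentions the webinar arm. Online training appears only as the effect to be validated and in connection with later randomized studies.
- Protocol: describes the randomization but gives no between-arm analysis.

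So nothing supplies it.

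**2. Can the pooled change stand in for it?** Let D1 and D0 be the mean changes in the two arms, with variances s²/n1 and s²/n0, N = n1 + n0, and pooled change wD1 + (1−w)D0 with w = n1/N. Its covariance with D1 − D0 is

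w·s²/n1 − (1−w)·s²/n0 = s²/N − s²/N = 0.

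With equal SDs, the pooled estimate carries no information about the arm difference.

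**3. What precision would the missing contrast have?** The plan has no figure to reproduce: there is no sample size, SD, effect size or allocation ratio. Assumptions: equal arms; SD 1 in both periods; correlation rho between a therapist's pre- and post-training case; pre-training gain known for all N; one post-training case from M = rN therapists. The values r = 0.65 and 0.50 borrow the SAP's retention marks. Those marks concern clinicians retained at 6 months, whereas the protocol accepts a post-training case up to 3 months after supervision, so r is an assumed share.

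- Arm contrast with a common pre-training mean: Var = 4(1−rho²)/M
- Pooled change: Var = (1−rho²)/M + (1−rho)²/N
- SE ratio = √[4(1+rho) / ((1+rho) + r(1−rho))]

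Example, rho = 0.3 and r = 0.65: √[5.2 / (1.3 + 0.455)] = √2.963 = 1.72.

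| Share with a post-training case | rho 0 | rho 0.3 | rho 0.7 |
|---|---|---|---|
| 100% | 1.41 | 1.61 | 1.84 |
| 65% | 1.56 | 1.72 | 1.89 |
| 50% | 1.63 | 1.78 | 1.92 |

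At 2:1 allocation the factor 4 becomes 4.5, and the range is 1.50 (r = 1, rho 0) to 2.03 (r = 0.5, rho 0.7). For a plain difference in change with complete pairs and equal arms, the ratio is √(4s²/N) / √(s²/N) = 2.0 at any rho.

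95% CI half-width, with n randomized and m = rn post-training cases per arm: t(0.975, 2m−3)·√[2(1−rho²)/m]. Example, n = 20, r = 0.65, rho = 0.3: m = 13, and 2.069 × √(1.82/13) = 0.77 SD. At rho = 0.3:

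| n per arm | 100% | 65% | 50% |
|---|---|---|---|
| 20 | 0.61 | 0.77 | 0.90 |
| 30 | 0.49 | 0.62 | 0.71 |
| 40 | 0.42 | 0.53 | 0.61 |

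**4. Which interval?** In simulation (8,000 runs, rho 0.3, 65% with a post-training case; 15, 30 and 45 randomized per arm), the normal-theory ML interval covered 0.908, 0.932 and 0.939. The t interval from the equivalent regression of post-training gain on arm and pre-training gain covered 0.949, 0.951 and 0.951.

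**The case against.** The strongest reply is that this is a feasibility study. Aim 1 is named as the overall aim, and mediators and moderators are left to later randomized studies. The commitment to compare arms stands in the SAP's own Aims section, so an analyst reading the whole document would know that the comparison is owed. This stands as to severity: what is missing is the specification of an exploratory estimate, not a confirmatory test.

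Three stronger readings are tempting, and the documents do not support them.

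- A reader might infer that the planned model excludes arm. The SAP lists no full set of fixed effects for any model; it gives a framework and a question. The text shows only that no arm term is named.
- A reader might infer that Aims 1, 3 and 4 share the fault. They promise no between-arm outcome analysis, so the mismatch lies within Aim 2 alone.
- A reader might infer that only a model with a common pre-training mean avoids bias from attrition. With dropout assumed to depend on pre-training gain in one arm only (log-odds slope 1 per SD, 30 per arm, rho 0.3, true difference 0), a change-score contrast in available pairs was off by −0.22 SD. But the SAP plans maximum likelihood on all available cases, and under that approach an ordinary arm-by-period contrast was also unbiased. The common mean improves precision (empirical SD 0.32 against 0.36).

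It is also fair to say that deleting the between-group wording from Aim 2 would make the SAP consistent. It would do so by giving up the randomized comparison.

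**Conclusion.** The point holds as a mismatch between Aim 2 and its own analysis. The aim commits to an arm comparison; the stated analysis does not describe one, and no other text does. Run as written, it yields no randomized contrast on the main Aim 2 outcome. This conclusion rests on the text alone.

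The precision figures show only what a repaired analysis could deliver. Under the assumptions given, the arm contrast has about 1.4 to 1.9 times the standard error of the pooled change, so in a small study its interval will be wide. The figures assume one post-training case per therapist and would change if two were used.

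Severity: should be fixed. The feasibility aim does not justify a higher grade.

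**What to change.** In the Aim 2 entry of the Data Analytic Plan:

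- Analyse therapists by allocated arm. Add period and period-by-arm to the planned ML mixed model for weight gain, and name the arm difference in post-training weight gain as the one arm contrast.
- Preferably constrain the arms to a common pre-training mean with an unstructured covariance for the two periods. This fits the design because the pre-training case is an eligibility item and eligibility is checked before randomization. An unconstrained arm-by-period contrast is acceptable but less precise.
- Report the contrast with a t-based 95% CI, as an estimate and not a powered test. Keep the before-to-after result separate.
- State which post-training case enters. The protocol's weight-change measure describes one per therapist, but its supervision paragraph allows up to two, with weight change reported for each. Alternatively, include both with a therapist random effect.

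The cost is SAP wording; no new data are needed. The downsides are:

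- The contrast is less precise than the pooled change.
- Therapists without a post-training case stay in the model but add nothing to the arm contrast itself unless attrition predictors are included.
- The common pre-training mean needs checking if any case supplied under the alternative eligibility route is treated after randomization.
- The contrast compares two active trainings, so it does not show by itself that training works.

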When the training is completed, therapists will proceed to schedule post- online supervision for a minimum of 1 case and a maximum of 2 cases over the course of 3 months with one of two clinicians at UCSF. At the 4 week treatment mark for each case, therapists will complete a self-report on FBT fidelity to key components and patient weight change. Therapist video skill assessments related to key components will take place at baseline and at the end of online ET-FBT and end of supervision. Once the therapist completes a minimum of one case, the therapist will receive CE credit and a certificate of completion of FBT training. Therapists who enter the online training protocol will be compensated for their time for the completion of all assessments (\$100 for each assessment point).

UCSF's role in research activities are as such: Two UCSF clinicians will be responsible for conducting individual work with each therapist participant weekly for 1 hour per week for 12 weeks during the supervision timepoint of the study. They will use the published supervision manual for FBT (Forsberg et. al) published by Guilford. They will rate fidelity using a therapist version of self-report (described below) and will rate the recorded responses to the

clinical vignettes (described below). They will have access to all of the fidelity assessments (the self-reports and the vignettes all outline below) in order to complete these ratings. Access will be through RedCap in order to make sure the data they receive is secure and HIPAA compliant in accordance with Stanford's IT recommendations. They will also know the patient weight change data (solely session 1 through 4 weights and dates taken no patient PHI will be collected in the study) as they need this information to teach the therapist using supervision.

Therapists will complete the following measures/assessments:

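### Aim 2 compares weight gain in different adolescents before and after training but names no adjustment for session 1 weight, which would mainly add precision

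*SAP*

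**What the plan says.** The SAP's list of aims sets two comparisons for Aim 2: "comparing patient weight gain from session 1 to 4 of FBT before and after training (target for training effect) and compared between randomized groups". The Data Analytic Plan then gives the method in one sentence: "using the same mixed effects modeling approach, we will examine whether the patient outcome (weight gain) significantly improves from pre to post training". The protocol, under Treatment Outcome Measures, calls weight change the main patient outcome for this aim.

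On where the data come from, the protocol says:

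- **Pre-training case.** To be eligible, therapists must "submit baseline data on weight gain from week 1-4 from a previously treated adolescent with AN they have treated in the last 6 months", or supply a case treated within 3 months of screening and before training starts.
- **Post-training case.** The weight change item says: "Weight change from sessions 1 to 4 will be collected on one adolescent patient with AN treated pre-training (baseline eligibility) and post online ET-FBT". The post-training case is one treated during supervision or within 3 months after it. Supervision covers "a minimum of 1 case and a maximum of 2 cases over the course of 3 months".
- **Patient data held.** The paragraph on UCSF's role describes the patient data as "solely session 1 through 4 weights and dates taken no patient PHI will be collected in the study".

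The only covariates the SAP mentions for the mixed models are clinician fidelity or competency and, as a sensitivity analysis under Aim 1, predictors of dropout: "we will conduct mixed effects analyses with and without including other possible predictors of attrition". Aim 4 does look at baseline predictors, but it is exploratory, and the measures the protocol assigns to it describe the therapist.

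**The concern.** The pre-post contrast is within therapist but between patients. A therapist effect in the mixed model absorbs stable differences between therapists. It does nothing about who the two adolescents were. If starting weight is related to early gain, leaving it out has two consequences.

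1. Variation in starting weight stays in the residual, and the estimate of the main patient outcome is less precise than the data allow. This applies to the pre-post contrast and to the comparison between randomized groups.
2. In the pre-post contrast, which has no control, a systematic difference in starting weight between periods would be attributed to training. The two cases do arrive by different routes: one is a recent case submitted to qualify for the study, the other is taken on after training. Where a therapist has two supervised cases, no rule says which one supplies the outcome.

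Session 1 weight is the only patient-level starting value the documents describe, and the plan gives it no role in the model.

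**Working it through.** **Plan's own figure.** There is none to reproduce. The documents give no sample size, SD, effect size or correlation for Aim 2. All inputs below are assumptions, shown over a range. A two-sided 5% level is stated only for the Aim 1 retention test and is assumed here.

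**Step 1: precision.** Let r be the correlation between session 1 weight and session 1 to 4 gain. After adjustment, residual variance is multiplied by 1 − r² and residual SD, hence interval width, by √(1 − r²). For scale, power is shown for a true difference of 0.5 SD with 30 pre and 30 post cases treated as independent groups, with the number per period needed for 80% power.

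| absolute r | 1 − r² | √(1 − r²) | interval narrower by | power | n per period |
|---|---|---|---|---|---|
| 0 (unadjusted) | 1.00 | 1.000 | – | 0.49 | 63 |
| 0.2 | 0.96 | 0.980 | 2% | 0.51 | 61 |
| 0.3 | 0.91 | 0.954 | 5% | 0.53 | 58 |
| 0.5 | 0.75 | 0.866 | 13% | 0.61 | 48 |

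These figures assume that starting weight is balanced across the groups compared. If the means differ by s SD, the variance of the adjusted contrast is also multiplied by 1 + s²/4. At s = 0.5 that is 1.0625, so the net variance is 0.91 × 1.0625 = 0.97 or 0.75 × 1.0625 = 0.80 of the unadjusted variance. The full precision gain and the full bias reduction are therefore not obtained together.

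**Step 2: bias in the pre-post contrast.** With no training effect, a systematic shift of s SD in mean starting weight moves mean gain by r × s, in SD of gain. At s = 0.5 this is 0.3 × 0.5 = 0.15 SD or 0.5 × 0.5 = 0.25 SD in absolute value. The direction depends on the signs of r and s, neither of which is known.

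Take a within-therapist correlation of 0.1, so that SE = √(2 × 0.9 / n). This is 0.300 for 20 therapists and 0.212 for 40. The chance that a two-sided 5% test rejects with no training effect is then:

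| absolute r | s | bias (SD) | 20 therapists | 40 therapists |
|---|---|---|---|---|
| 0.2 | 0.25 | 0.05 | 5.3% | 5.6% |
| 0.3 | 0.5 | 0.15 | 7.9% | 10.9% |
| 0.5 | 0.5 | 0.25 | 13.3% | 21.8% |

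**Step 3: how unusual is a 0.5 SD shift?** If starting weights are independent between periods, the chance difference in means has SD √(2/n): 0.32 for 20 therapists and 0.22 for 40. A shift of 0.5 is 0.5/0.32 = 1.6 or 0.5/0.22 = 2.2 of these (unrounded SDs give the same), so it is larger than chance usually gives. The usual standard error already allows for chance imbalance; only a systematic shift is bias.

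**Step 4: is the covariate available?** The statement that session 1 to 4 weights and dates are held sits in the paragraph on supervisors, who need them for teaching, and is clearest for supervised cases. For the pre-training case the eligibility paragraph asks for weight gain and the outcome item for weight change. Neither says that the session 1 weight itself is entered.

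**The case against.** The strongest reply is that this is a feasibility study with a one-sentence plan that does not exclude covariates, and that a 5% to 13% narrower interval is modest. Both statements are true. But weight gain is named as the main patient outcome, and a covariate fixed in advance avoids a data-driven choice later, at almost no cost.

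Four further objections limit what can be claimed.

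- **Availability.** A reader might infer that session 1 weight is already in hand for every case. The documents do not establish this for the pre-training case, so confirmation is part of the fix.
- **Bias.** A reader might infer that a pre-post improvement would probably be an artefact of starting weight. The documents do not support that. They give no correlation and no evidence of a shift, and the different routes of entry make one possible without giving its size or direction.
- **Completeness.** A reader might infer that adjustment would remove case-mix confounding. Patient height, age and sex are not listed as collected. Kilograms at session 1 mix body size with degree of underweight, so the covariate is only a partial proxy.
- **The randomized comparison.** Between arms, randomization of therapists leaves starting-weight differences mainly to chance, so the gain there is mainly precision. Post-training cases are, however, taken on after randomization, which is one reason to show the unadjusted result as well.

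**Conclusion.** The point holds as a recommended improvement to the Aim 2 model. The gains before and after training come from different adolescents, and no adjustment for starting weight is named. The main benefit is precision: 9% to 25% less residual variance if the absolute correlation is 0.3 to 0.5, about 4% if it is 0.2, and the loss of one degree of freedom if it is zero.

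Protection against bias is secondary and confined to the uncontrolled pre-post contrast. The 0.15 to 0.25 SD figure needs both an assumed correlation and an assumed systematic 0.5 SD shift; with the smaller inputs shown, the effect on the error rate is slight. Because adjustment for weight in kilograms can only reduce such bias, the contrast remains uncontrolled after adjustment and should be described that way.

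**What to change.** Add to the SAP under Aim 2 that the model includes, as an occasion-level covariate, the session 1 weight of the case supplying each gain. Each therapist then has separate values for the pre- and post-training cases. Apply this to the pre-post contrast and to the comparison between randomized groups. Also:

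- report mean session 1 weight by period and arm;
- show the unadjusted result beside the adjusted one;
- describe the pre-post contrast as uncontrolled;
- confirm that the session 1 weight itself, and not only the gain, is recorded for the pre-training case.

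The cost is a few lines in the SAP and one degree of freedom. If the pre-training form records only the gain, it needs one added item.

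Two extensions are optional and not part of this recommendation: carrying the covariate into the Aim 3 latent slope model, which changes that model's specification, and adding patient age, sex and height to the form, which widens the patient data the protocol now limits to weights and dates.

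### Aim 3: with one pre- and one post-training weight gain per therapist, the planned slope correlation is not identified unless the patient residual variance is fixed, and the SAP states no such constraint

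*SAP*

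**What the plan says.** The Aim 3 paragraph of the SAP's Data Analytic Plan asks how change on the clinician side relates to change in patient weight gain. It places this in a latent variable framework, to be carried out "by formally relating the parallel longitudinal processes (esp. by correlating the slopes) of patient and clinician outcomes". Clinician outcomes are measured three times ("3 assessments: 0 (pre), 3 and 6 month", under Aim 1).

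The patient outcome is defined in the protocol under Treatment Outcome Measures: "Weight change from sessions 1 to 4 will be collected on one adolescent patient with AN treated pre-training (baseline eligibility) and post online ET-FBT". I read this as two values per therapist. They come from two different adolescents, because the first is an eligibility case treated before training and the second is treated during supervision or in the three months after it.

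The protocol's description of supervision is wider. Supervision is "for a minimum of 1 case and a maximum of 2 cases over the course of 3 months", and "At the 4 week treatment mark for each case, therapists will complete a self-report on FBT fidelity to key components and patient weight change". The paragraph on the collaborating institute's role says that supervisors will know patient weight data, "solely session 1 through 4 weights and dates taken".

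For Aim 3 the SAP states no residual-variance constraint, no difference score, and no use of a second case or of session-level weights.

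**The concern.** A correlation of slopes needs the variance of each slope. Three assessments can supply it for the clinician process. Two values cannot supply it for the patient process when a residual variance is also estimated. Here the residual is not minor measurement error. The two gains belong to different adolescents, so ordinary patient-to-patient variation is the very quantity that cannot be told apart from true therapist change.

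The SAP presents Aim 3 as the validation of the training target and as groundwork for mediation analyses in later randomised studies. Those studies would use the size of the association, and the size of the correlation is what the plan leaves to an unstated modelling choice.

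**Working it through.** The documents give no sample size, effect size or power for Aim 3, so there is no figure of the plan's own to reproduce. The check is one of identification.

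**Inputs.** Clinician occasions at 0, 3 and 6 months (SAP, Aim 1). Patient occasions pre and post (protocol, Treatment Outcome Measures; the SAP's Aim 2 uses the same contrast). Assumed, because the SAP does not specify them: linear growth, one residual variance per process, and residuals uncorrelated across processes.

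**1. Patient process alone.** Write the pre-training gain as Y0 = I + e0 and the post-training gain as Y1 = I + S + e1. Let vI and vS be the variances of I and S, c their covariance, and r the residual variance.

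- Var(Y0) = vI + r
- Cov(Y0, Y1) = vI + c
- Var(Y1) = vI + 2c + vS + r

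There are three moments and four unknowns. Change (vI, c, vS, r) by (+1, −1, +2, −1) times any small amount. Var(Y0) moves by 1 − 1 = 0, the covariance by 1 − 1 = 0, and Var(Y1) by 1 − 2 + 2 − 1 = 0. Different slope variances fit the data equally well.

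**2. Adding the clinician process.** Five observed variables give 5 × 6 / 2 = 15 variances and covariances. Four latent terms give 4 × 5 / 2 = 10 parameters, plus 2 residual variances, which makes 12. The numerical rank is 11, and the deficiency lies wholly in vI, c, vS and r. With means included there are 20 moments, 16 parameters and rank 15. The clinician data do not repair the patient side.

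**3. What is identified.** With D = Y1 − Y0, I cancels and Cov(D, clinician slope) = Cov(S, clinician slope). The slope covariance, its sign and its test against zero do not depend on r.

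**4. What is not.** Var(D) = vS + 2r. If s = 2r / Var(D) is the share called residual, the correlation is the residual-zero correlation divided by √(1 − s). Starting from an assumed 0.30:

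| s (assumed) | Correlation |
|---|---|
| 0 | 0.30 |
| 50% | 0.30/√0.50 = 0.42 |
| 75% | 0.30/√0.25 = 0.60 |
| 90% | 0.30/√0.10 = 0.95 |

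**5. Fixing r at 0.** The model is then identified (15 parameters, rank 15, means included), and the slope is the difference score. If the true between-patient SD is k times the SD of therapist change, the correlation is multiplied by 1/√(1 + 2k²): 0.58, 0.33 and 0.23 for k = 1, 2 and 3 (assumed values).

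**6. A second post-training case.** One pre and two post values give 21 variances and covariances, 12 parameters and rank 12 (with means: 27, 16 and 16). The two post cases separate post-training residual from therapist variance, but vI is still confounded with the pre-training residual unless the two residual variances are equal. The information comes only from therapists with two cases.

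**7. Consequence for the observed difference score.** Simulation with true correlation 0.5, clinician-slope reliability 0.7 and two-sided alpha 0.05, all assumed. The expected observed correlation is 0.5 × √(0.7 × reliability of D).

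| Reliability of D | Expected correlation | Power N=20 | N=40 | N=60 |
|---|---|---|---|---|
| 1.0 | 0.42 | 47% | 78% | 93% |
| 0.5 | 0.30 | 25% | 46% | 64% |
| 0.3 | 0.23 | 16% | 30% | 44% |

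With a true correlation of zero, rejection rates were 4.7% to 5.5%.

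**The case against.** A reader might infer that Aim 3 cannot be estimated at all. The documents do not support that. The association can be estimated as a covariance and tested, and a difference score gives a valid test of no association. The SAP's target is change against change, which a difference score fits, and the SAP nowhere says that the patient residual will be left free. It is fair to call this silence on a parameterisation.

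A reader might also infer that any reported correlation would owe nothing to the data. That too goes too far: only the standardised scale depends on the fixed residual.

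Nor is it settled that only two values exist per therapist, since the supervision text allows a second post-training case with its weight change. That helps only under equal residual variances and only through therapists with two cases, and the SAP does not plan to use it. Session-level weights would address measurement error within a patient but not variation between patients.

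The multipliers above rest on assumed shares, SD ratios, reliabilities and sample sizes. They show sensitivity and do not predict this trial's result.

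What remains is that the SAP names a correlation of slopes, and the data as defined cannot supply it without a constraint that sets its size and that nobody has written down.

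**Conclusion.** The concern holds in limited form. Under the protocol's outcome definition, the patient slope variance is not identified with a free residual, so the standardised slope correlation is not identified either. The slope covariance is. Fixing the residual at 0 yields a correlation attenuated by patient-to-patient variation, by an amount that cannot be computed from the documents.

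The rank result rests on two common patient occasions, linear growth and one residual variance per process. Relaxing the last would only add unknowns.

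This should be fixed before analysis, but it does not threaten the study. Feasibility is the overall aim, and neither the retention test in Aim 1 nor the pre-to-post weight comparison in Aim 2 is affected.

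**What to change.** Rewrite the Aim 3 paragraph of the SAP as follows.

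- Replace the latent patient slope with a regression of post-training patient weight gain on clinician change in fidelity or competency, adjusted for the pre-training patient's gain. Report the unstandardised coefficient with its 95% CI. If the change-with-change question is to be kept, use the post-minus-pre difference as the outcome. The two answer different questions, so name one in advance.
- Keep latent slopes only for clinician measures with three assessments. Supervisor-rated fidelity, completed only at the end of supervision, has none.
- Reconcile the protocol's outcome definition (one post-training patient) with its supervision text (one or two cases). State how many post-training cases per therapist enter the analysis and, if two are possible, how they are chosen or combined.
- State that no error-free (disattenuated) slope correlation will be claimed.

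The cost is about one paragraph of SAP text, a clarifying sentence in the protocol and no new data. The downsides are that no latent correlation is reported and patient noise widens the confidence interval. Random noise in the outcome does not bias an unstandardised coefficient, but error in observed clinician change may attenuate it.
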